#### 7.3.15.2 SUBJECT REPLACEMENT

Subjects may be replaced if they are screen failures.

Version 5.0 08-Jun-2022

# 7.3.15.3 LOST TO FOLLOW-UP

The effort to obtain follow-up information should include 3 attempts to make contact with the subject via telephone or text. All contact efforts to obtain follow-up information should be documented in ePRO.

## 7.4 MONITORING

All source data and documentation will be reviewed for completeness and appropriateness by investigative staff.

The Principal Investigator and Climb will permit the Sponsor (or designee) and the FDA to inspect source documentation and data for this study. These inspections are for the purpose of verifying adherence to the protocol and the completeness and accuracy of the data recorded in ePRO.

#### 7.4.1 Source Data and Documentation

For this patient-reported decentralized clinical trial, source data is defined as all information in original records of clinical findings, observations, or other activities in a clinical investigation, necessary for the reconstruction and evaluation of the clinical investigation. Data entered into ePRO by subjects and/or investigative staff will be considered one form of source data for this study.

Source documents are defined as printed, optical, or electronic documents containing source data, e.g., prescriptions for the device, device accountability records, and any medical records kept by the investigative staff in support of this clinical investigation.

#### 7.4.2 Audits and Inspections

The FDA and the Notified Body have the right to conduct an audit of the clinical investigation to ensure that the clinical investigations was, in fact, performed by the investigative staff and that the data reported in support of a marketing application accurately reflects the data in the records. The authority may also inspect such studies to verify that the clinical investigation was conducted in accordance with national regulations relating to the IRB and informed consent. It is the joint responsibility of the Sponsor and the Principal Investigator to ensure that the clinical investigation has been conducted in line with all national and local regulations.

In the event that the FDA or Notified Body desires to inspect this clinical investigation, the Sponsor, Principal Investigator, Climb, and NAMSA will permit authorized inspectors to inspect all facilities and records relating to the clinical investigation and aid the Inspector to perform the audit in a timely fashion.

Separately, during the conduct of this clinical investigation, Fisher Wallace may appoint Quality Assurance (QA) personnel to audit the administration and conduct of the clinical investigation.

# 8 STATISTICAL DESIGN AND ANALYSIS

Statistical analysis for the study will focus on the randomized comparison of groups for study endpoints. Key elements of the planned statistical analysis are outlined below. Additional details, including more

details regarding plans for analysis populations, subgroups, secondary endpoints, handling missing data, and sensitivity analyses will be provided in a separate standalone Statistical Analysis Plan.

# 8.1 ANALYSIS POPULATION

The primary analysis will be based on intent-to-treat, with subjects analyzed as randomized regardless of treatment actually received.

# **8.2 DESCRIPTIVE STATISTICS**

Continuous data will be summarized with mean, standard deviation, median, minimum, maximum, and number of evaluable observations. Categorical variables will be summarized with frequency counts and percentages. Confidence intervals may be presented, where appropriate, using the t-distribution for continuous data and Clopper-Pearson Exact method for categorical variables.

# **8.3** ANALYTICAL PROCEDURES

The primary endpoint is the change in BDI-II at week 2 compared to baseline. Analysis will be based on a linear model for change, adjusted for each subject's baseline value. The mathematical statement of the null and alternative hypothesis for primary endpoint is:

Ho: B2  $\leq 0$ 

Ha: B2 > 0 where B2 represents the regression coefficient from the linear model corresponding to study arm, parameterized so a regression coefficient greater than zero represents a greater mean change for the treatment group compared to the control group. The general form of the linear model for each endpoint is:

 $\Delta Y = B0 + B1Y0 B2*X$ 

where  $\Delta Y$  is the change in outcome from baseline at week 2, B0 is the intercept term, B1 is the coefficient for the subject's baseline value Y0, and X is the treatment group indicator (1 = treatment, 0 = sham). Multiple imputation will be employed to address missing data.

Study success will be based on successful rejection of the null hypothesis for the primary endpoint.

Subgroup analysis will be provided based on sex and race as well as potentially other baseline factors, including baseline BDI-II score.

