	
 
13. Legally blind and/or deaf and without in-home care service to assist with study participation
 
14. Meets M.I.N.I. assessment criteria for, or has been diagnosed with, any of the following: Bipolar I disorder, bipolar II disorder, other specified bipolar and related disorder, panic disorder, agoraphobia, social anxiety disorder (social phobia), obsessive-compulsive disorder, posttraumatic stress disorder, alcohol use disorder in the past 12 months, substance use disorder (non-alcohol) in the past 12 months, any psychotic disorder (e.g., schizophrenia, schizoaffective disorder), major depressive disorder with psychotic features, anorexia nervosa, bulimia nervosa, binge-eating disorder, generalized anxiety disorder, any cognitive or developmental disorder (e.g., autism, Down's Syndrome), any personality disorder or psychiatric disorder that may interfere with study participation
 
15. Current participation in another investigational study or participated in an investigational study within the past 30 days
 
16. In the opinion of the investigator, may not be able to comply with study requirements
 
17. Any employee, family member, or personal associate of the Sponsor or their designees conducting the study
 

Target Population/ Sample Size	Adults ages 21-65 years. A total of 250 evaluable subjects (approximately 1:1 allocation) will be included in this study. Subject will be located in the United States and have a diagnosis of moderate to severe Major Depressive Disorder.
Number of Site(s)	One investigative site in the US with subject activities conducted via a decentralized/remote method.
Study Duration	Estimated subject participation time is approximately 6 weeks: 2-week lead-in period followed by 4 weeks of treatment.
Statistical Methods	Continuous data will be summarized with mean, standard deviation, median, minimum, maximum, and number of evaluable observations. Categorical variables will be summarized with frequency counts and percentages. Confidence intervals may be presented, where appropriate, using the t-distribution for continuous data and ClopperPearson Exact method for categorical variables. The primary endpoint is the change in BDI-II at week 2 compared to baseline. Analysis will be based on a linear model for change, adjusted for each subject's baseline value, comparing the randomized groups.

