# 7.2.3 Point of Enrollment

A subject is considered enrolled in this study after they have signed the informed consent form and consented to allow the use of their data collected during the pre-screening process for study evaluations.

If either of these conditions are not met, the subject will be considered a screen failure if the ICF has been signed, or a pre-screen failure if the ICF has not yet been signed.

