## 7.3.4 Screening Lead-In and Baseline

Upon signing the informed consent form, subjects will begin the screening lead-in period of 14-days minimum. No data will be collected from the subject during this time; however, the data collected during pre-screening will be saved in ePRO as study eligibility data.

After 14 days of lead-in time, subjects will be prompted to retake the BDI-II and PHQ-9 assessments in ePRO. Subjects will also take a QIDS-SR assessment in ePRO. A subject must have a BDI-II score between 20 and 63, indicating moderate to severe MDD, at both initial pre-screening and baseline to participate in the study.

If the BDI-II assessment score is not within the moderate to severe MDD range, the subject's health will be considered insufficiently stable for study entry. The subject will be notified that they are no longer eligible for study participation and they will be considered a screen failure.

If the screened subject's data is within the moderate to severe MDD range for the BDI-II assessment, the subject will advance to scheduling a meeting with a clinician from the investigative team.

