#### 8.5 SAMPLE SIZE CALCULATION AND JUSTIFICATION

A total of 250 evaluable subjects (in a 1:1 allocation ratio) will provide 80% power assuming a population mean difference between groups of 3.2 and a common standard deviation of 9 based on a two-sided twosample t-test with an alpha of 0.05. Previous data suggests the standard deviation for 2 week improvement to be approximately 6.5; however, a conservative estimate of 9 was used for these calculations. If the observed standard deviation is less than 9, a smaller effect size will provide 80% power. In addition, this calculation is conservative since the planned test adjusting for baseline is expected to provide additional power. Sample size calculations were performed using PASS 2021 (NCSS, LLC). While some amount of missing data is expected, the primary analysis will be based on the randomized cohort of subjects and will employ multiple imputation to mitigate the impact of missing data.

The sample size for the study is practically constrained by regulatory requirements for timely submission and the impact of the COVID-19 pandemic. Accordingly, while the final formal analysis is planned for the final planned sample size, circumstances may dictate initial regulatory submission based on data available with supplemental updates provided later based on the final data set. Since the formal analysis will be based on the final planned sample size, there are no alpha implications.

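### The primary model in 8.3 leaves out the pre-screening BDI-II, a second pre-randomisation score that every eligible subject has: a small missed gain in precision, not an error

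*Combined protocol and SAP*

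**What the plan says.** Section 8.3 defines the primary analysis: "Analysis will be based on a linear model for change, adjusted for each subject's baseline value". The equation there has an intercept, the baseline value Y0 and the treatment indicator X, and is offered as the general form for each endpoint. The Statistical Methods row of 1.3 agrees: "adjusted for each subject's baseline value, comparing the randomized groups".

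Three places establish that an earlier score on the same scale exists for everyone:

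- Section 7.3.4 makes it an entry requirement: "A subject must have a BDI-II score between 20 and 63, indicating moderate to severe MDD, at both initial pre-screening and baseline".
- The same section keeps it: "the data collected during pre-screening will be saved in ePRO as study eligibility data".
- Section 7.2.3 makes permission to use it part of the definition of enrolment; the subject must have "consented to allow the use of their data collected during the pre-screening process for study evaluations".

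Section 8.5 already counts on covariate adjustment: "this calculation is conservative since the planned test adjusting for baseline is expected to provide additional power". No section uses the pre-screening BDI-II in an analysis. Section 8 defers further detail to a standalone SAP, which is not among the documents I worked from.

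**The concern.** A covariate measured before randomisation and correlated with the outcome reduces residual variance at almost no cost. The strongest candidate is usually an earlier measurement of the outcome itself. This trial has two, both complete by design, and the stated model uses one.

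What is at stake is the width of the confidence interval for B2 and, to a lesser degree, power. Timing matters too: a covariate named before unblinding is unremarkable, whereas one added afterwards in a pivotal trial invites challenge.

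**Working it through.** **Plan's own figure.** With 125 per arm, difference 3.2 and SD 9, the noncentrality is 3.2 / (9 × √(2/125)) = 3.2 / 1.138 = 2.81. Two-sided 0.05 (one-sided 0.025) gives 79.96% power by the noncentral t, so the stated 80% reproduces. That calculation is for an unadjusted t-test, and I claim no gain at SD 9.

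**Formula.** Let S be the pre-screening score, Y0 baseline and W week 2. Adding S to a model with Y0 multiplies the interval width by √(1 − p²), where

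p = (r_SW − r_SY·r_YW) / √[(1 − r_SY²)(1 − r_YW²)].

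The documents give none of these correlations. All values below are assumptions, before any selection at entry.

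- Equal correlations r: the ratio is √(1 + 2r)/(1 + r). For r = 0.6, √2.2/1.6 = 0.927, a cut of 7.3%. For r = 0.7 the cut is 8.9%; for r = 0.8 it is 10.4%.
- Partial decay, r_SY = r_YW = 0.7 and r_SW = 0.6: p = (0.60 − 0.49)/0.51 = 0.216, a cut of 2.4%.
- Weaker week-2 correlation after treatment or sham, r_SY = 0.7 and both others 0.5: p = (0.50 − 0.35)/√(0.51 × 0.75) = 0.243, a cut of 3.0%.
- AR(1), r_SW = r_SY × r_YW: p = 0, no cut.

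**Allowing for the entry rule.** A floor of 20 at both looks restricts range and weakens correlations. I simulated rounded trivariate normal scores limited to 0–63 and selected on S ≥ 20 and Y0 ≥ 20. The assumed mean was 26–30, the SD 8–10 and r 0.6–0.8.

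| Correlation pattern | Residual SD, Y0 only | Interval narrows by | Power gain for 3.2 (points) |
|---|---|---|---|
| Equal | 4.7–7.9 | 5–9% | 0.0–3.2 |
| Intermediate, r_SW = (r + r²)/2 | 4.8–8.0 | 1–2% | 0.0–0.8 |
| AR(1) | 4.8–8.0 | 0% | 0 |

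With no decay but both week-2 correlations 0.2 below r_SY, the narrowing is about 1.6–2.8%. A smaller shortfall falls between that and the equal-correlation row.

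**At the plan's own SD.** Section 8.5 reports: "Previous data suggests the standard deviation for 2 week improvement to be approximately 6.5". In settings whose change SD is 6.0–7.0, the residual SD after Y0 is 5.6–6.4. At 6.41 the noncentrality is 3.2 / (6.41 × 0.1265) = 3.95, and power is 97.6%; at the lower end it is 99.4%. The added covariate gains 0.4–1.0 points with equal correlations, 0.1–0.3 with intermediate decay and none under AR(1).

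**Trial-level check.** N = 250, with 20,000 simulated trials per setting and true difference:

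| Setting (mean/SD/r) | Mean half-width, Y0 only → with S | Power, Y0 only → with S |
|---|---|---|
| Equal, 30/10/0.6 | 1.963 → 1.853 | 0.893 → 0.923 |
| Equal, 28/8/0.7 | 1.405 → 1.304 | 0.994 → 0.998 |
| Intermediate, 28/10/0.7 | 1.773 → 1.748 | 0.944 → 0.951 |
| AR(1), 26/10/0.6 | 1.998 → 2.002 | 0.880 → 0.878 |

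One-sided type I error was 0.0247–0.0255 with Y0 alone and 0.0239–0.0257 with both scores. Mean B2 lay within 0.01 of the true value in both models.

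**The case against.** The case against acting is fair in several respects. Change adjusted for baseline is a standard, valid primary model, and nothing in the protocol promises the most efficient one. Near an SD of 6.5, power for 3.2 has almost no room to rise. The upper end of the range needs week-2 scores to correlate with pre-screening as strongly as with baseline. That is doubtful: the lead-in is only a minimum of 14 days; interview, randomisation, shipment and training come between baseline and first use, with no stated maximum; and section 4.2 reports high placebo response in the earlier trial. All of this stands and makes the lower part of the range more likely.

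The unseen SAP could also name further covariates, since section 8 calls itself an outline of key elements. However, the topics it lists for deferral do not include covariates of the primary model, and 8.3 writes that model out in full.

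Power is near its ceiling only for a true difference of 3.2. For a smaller difference it is not, and a narrower interval helps interpretation at any effect size.

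A reader might go further and infer that the lead-in statement in 7.1.2 about regression to the mean needs correcting. The documents do not support that as a finding. The section says only that the lead-in should minimise such bias, and any residual drift affects both arms alike. Section 8 rests on the contrast between arms: "Statistical analysis for the study will focus on the randomized comparison of groups for study endpoints". The share removed also depends on the comparator. Under AR(1) it is negative (−18% to −28%) against a floor at baseline only, but about 22–33% against a pre-screening floor with change measured from pre-screening.

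**Conclusion.** The point holds as a missed efficiency of low priority. The stated primary model omits a pre-randomisation BDI-II score that is complete by design, stored and consented for use.

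The gain rests on assumed correlations: about 5–9% narrower intervals if all are equal at 0.6–0.8, about 1–3% with some decay or a week-2 correlation about 0.2 weaker, and none under AR(1). Near the SD in 8.5, the power gain for 3.2 is at most about 1 point, so the benefit is mainly a modestly narrower interval.

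Two stronger readings should be resisted. One is that the primary analysis is biased or its error rate inflated without the extra covariate; randomisation protects B2 and the type I error either way. The other is that a gain near 9% can be counted on; the documents contain nothing that fixes the correlations, and zero is within the range.

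**What to change.** Before unblinding, change 8.3 and the Statistical Methods row of 1.3 so that the BDI-II change models read

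ΔY = B0 + B1·Y0 + B2·X + B3·Yscreen,

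with Yscreen defined as the pre-screening BDI-II held in ePRO at enrolment and the other terms as now. Keep the model without Yscreen as a sensitivity analysis. Include Yscreen in the imputation model, so that the planned multiple imputation matches the analysis model.

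Because 8.3 gives one form for each endpoint, state the scope. The PHQ-9 models may use that scale's own pre-screening score. The QIDS-SR models should not be given an earlier score of their own, because QIDS-SR is first collected at baseline.

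The cost is wording, handled through the amendment route in section 10, and one degree of freedom. If the score adds nothing, the interval is about 0.2% wider (1.998 to 2.002 in the AR(1) check). Hypotheses, alpha, sample size, eligibility, visits and data collection do not change.

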More than 40% of the patients had a decrease of 50% in BDI-II or more. Due to high levels of placebo response, the between group difference in BDI-II change was -0.8 (p = 0.496). Significantly, and despite the fairly large drop in BDI-II during the first four weeks in the sham arm, the switch to active treatment was associated with additional improvement (BDI-II decrease from week 4 to 8 of 3.6 points) beyond what they had experienced during the first four weeks, while the Immediate Treatment arm only showed minimal additional improvement in this period (BDI-II decrease of 0.6 points, p < 0.01), representing an improvement of more than 15% from BDI-II scores from the end of the sham period. Thus, the data demonstrate the effectiveness of the FW-200 in treating depression.

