# 8.4 SIGNIFICANCE LEVEL AND POWER OF THE PRIMARY ENDPOINT AND OVERALL STATISTICAL TESTING STRATEGY

The primary endpoint analysis will be performed at the one-sided 0.025 alpha level. Any other p-values and confidence intervals will be based on a nominal two-sided 0.05 alpha level (or equivalently a one-sided 0.025 alpha level as appropriate) without adjustment for multiple comparisons.

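### Is the one-sided primary test in section 8.3 written in the wrong direction, so that a fall in BDI-II on the active device could not count as success?

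*Combined protocol and SAP*

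**What the plan says.** Section 8.3 sets the endpoint: "The primary endpoint is the change in BDI-II at week 2 compared to baseline". The dependent variable of the linear model "is the change in outcome from baseline at week 2", and "X is the treatment group indicator (1 = treatment, 0 = sham"). The model also adjusts for the baseline score. The alternative is "Ha: B2 > 0 where B2 represents the regression coefficient from the linear model corresponding to study arm", with the model "parameterized so a regression coefficient greater than zero represents a greater mean change for the treatment group compared to the control group". The decision rule is "Study success will be based on successful rejection of the null hypothesis for the primary endpoint", and section 8.4 adds that "The primary endpoint analysis will be performed at the one-sided 0.025 alpha level".

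No subtraction order is given for the change score. The printed equation has no operator between the baseline term and the arm term. That may be lost in the text conversion, so nothing is built on it here.

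Section 8.5 sizes the trial on a positive difference of 3.2 and describes the outcome whose SD it cites as improvement over two weeks. Section 4.2, on the earlier trial, reports that "the between group difference in BDI-II change was -0.8 (p = 0.496").

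**The concern.** Change from baseline is commonly computed as follow-up minus baseline. BDI-II falls when depression lifts, so on that convention a working device gives a negative change and a negative B2. The printed alternative is B2 > 0, so the test would look in the tail where patients on the active device do worse.

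The -0.8 in section 4.2 seems to support this, because it looks like a small advantage for active treatment written with a minus sign. The parameterisation clause seems not to help, because it speaks of a greater change and not of a greater improvement.

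This is the only success criterion and it is one-sided. A wrong sign would therefore not be caught by the test itself. If the sign were chosen after unblinding, the effective one-sided level would rise from 0.025 to 0.025 + 0.025 = 0.05.

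**Working it through.** **Inputs.** Difference 3.2, common SD 9, 250 evaluable subjects at 1:1 (125 per arm), two-sided 0.05 for sizing (section 8.5). One-sided 0.025 for the test (section 8.4). Arm coding and hypotheses from section 8.3.

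**The plan's own figure.** SE = 9 × √(2/125) = 1.138. Standardised effect = 3.2 / 1.138 = 2.811. Power = Φ(2.811 − 1.960) = Φ(0.851) = 80.3%. The noncentral t with 248 degrees of freedom gives 79.96%. The stated 80% is reproduced, and using one-sided 0.025 in place of two-sided 0.05 makes no visible difference.

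**Probability of meeting Ha: B2 > 0 under each subtraction order.**

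| True effect on BDI-II | Change = week 2 − baseline | Change = baseline − week 2 |
|---|---|---|
| 3.2-point benefit | P(Z > 1.960 + 2.811) = 9.2 × 10⁻⁷ | 80.3% |
| none | 2.5% | 2.5% |
| 3.2-point harm | 80.3% | 9.2 × 10⁻⁷ |

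A simulation of the baseline-adjusted model agrees. It used 20,000 trials per scenario and assumed baseline mean 32 and SD 8 (held to 20–63), and residual SD 9. In the order of the table, the first column gave 0 rejections, 2.55% and 79.6%. The second gave 79.7%, 2.28% and 0 rejections.

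The arithmetic behind the concern is therefore right, but it applies to the first column only. The question is which column the plan describes.

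**Setting the sections side by side.**

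1. Section 8.3 fixes the arm coding and says what a positive coefficient is to mean: more change on active than on control. In everyday use, the arm whose scores fell further changed more. That is the second column.
2. Section 8.5, which sizes this same comparison, gives the difference as +3.2 and calls the two-week quantity an improvement. That also fits the second column.
3. Sections 6.1 and 6.2 state the aim of showing that the device is effective and improves symptoms. The first column would make worsening on the device the alternative hypothesis of a pivotal effectiveness trial, which contradicts that aim.
4. The -0.8 in section 4.2 belongs to a different, completed trial. The text does not say which arm was subtracted from which or how change was signed. The same section reports within-arm change as positive decreases (10.4, 3.6 and 0.6 points). Usage there is mixed and cannot define the variable in section 8.3.

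**Secondary scales.** Section 8.4 puts other p-values at nominal two-sided 0.05, or one-sided 0.025 where appropriate. A two-sided p-value is the same whichever way the score is subtracted.

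**The case for a change.** The strongest case for a change is that a one-sided pivotal test should state its direction in a form that needs no interpretation. Read algebraically, −7 is greater than −10, so under week 2 minus baseline the parameterisation clause is satisfied by the arm that improved less. The clause settles the direction only for a reader who already takes change to mean reduction. Elsewhere, in the responder definition and in section 8.5, the protocol writes improvement when it means improvement, but section 8.3 writes change. Section 8.5 also allows an initial regulatory submission on the data then available, so the convention should be settled before anyone sees results. One added line would do it.

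Some of this stands. The subtraction order is not written, follow-up minus baseline is a common default, and Section 8's list of topics left to a separate SAP does not name the sign of the primary change score. A sentence defining it would be good drafting.

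It does not follow that the test is reversed, or that its level is at risk. Which direction is benefit on BDI-II is fixed by the instrument, and section 4.2 itself treats a decrease as evidence of effect. An analyst has no free choice to make after unblinding. Nobody could present higher depression scores on active as success, and a lower mean on active meets the stated meaning of a positive coefficient once change is taken as reduction. The doubling of alpha needs a sign chosen from the data, and nothing in the plan points to that.

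**Conclusion.** The concern does not hold as an error in the primary test. The 1-in-1,000,000 and 80% figures are correct, but only if change is assumed to be week 2 minus baseline, which the protocol does not state and which conflicts with the study's aim. Taken together, the parameterisation clause in section 8.3, the positive 3.2 and the wording in section 8.5 lead to change as reduction. On that reading a 3.2-point benefit has about 80% power, a harm of the same size essentially never succeeds, and the one-sided level is 0.025.

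This is a gap in wording that analysts would fill sensibly. Filling it leaves alpha, the 250 subjects, power and the result unchanged. The conclusion assumes that the analysis follows the stated meaning of a positive coefficient, with greater change read as greater reduction in BDI-II. No change to the plan is called for.
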